## STUDY SCHEDULE OF EVENTS

**Table 1: Schedule of Events**

Tests	Screen (-10 wk to -1d)	Day 0	8-14 days post dose 1 Phone Call	Week 4 (± 7 days)	8-14 days post dose 2 Phone Call	Week 12 (± 7 days)	Week 15 (± 7 days)	Week 24 (± 7 days)	Week 27 (± 7 days)	Week 38 (± 7 days) Phone Call	Week 48 (± 7 days)	Week 52 (± 14 days)	Week 74 (±14 days)	Week 78 (± 14 days)	Week 96 (± 14 days)	Week 100 (± 14 days)
Informed consent	X															
Medical History/Demographics	X															
Medications (prior/concomitant)	X	X							X							
Socio-behavioral assessment	X										X					X
Inclusion/Exclusion criteria	X	X														
Randomization		X														
Physical exam (PE)/assessment a	X	X		X		X		X	X		X	X	X	X	X	X
Vital signs	X b	X		X		X		X	X		X	X	X	X	X	X
Screening safety (12 lead ECG, labs) c	X															
Pregnancy Testing d	X	X		X		X		X	X		X	X	X	X	X	X
HIV Ab by ELISA	X															
Blood immunologic samples	X e	X e					X e		X f		X e		X e		X e	
HLA testing g									X							
Cervical cytology, ThinPrep™ h	X								X		X		X		X	
OP rinse, vaginal, and intra-anal swabs		X							X		X		X		X	
Cervical colposcopy	X														X	
Vulvoscopy i	X	X		X		X			X		X		X		X	
Vulvar lesion standardized photography j	X	X		X		X			X		X		X		X	
Biopsy k	X										X		X		X	
Vulvar HPV genotyping l	X										X		X		X	
Inject VGX-3100 +EP m		X		X		X		X				X m		X m		
Post treatment reaction assessment		X		X		X		X				X		X		
Dispense imiquimod + distribute imiquimod dosing log n		X		X		X										
Review imiquimod dosing log and usage				X		X		X								
Distribute Participant Diary (PD)		X		X		X		X				X		X		
Review PD o			X		X		X		X				X		X	
Adverse Events	X															X
Ultrasound Measure of skin-to-muscle and related thicknesses	X															
Patient Reported Outcomes (PROs) p		X	X	X	X	X	X	X	X		X	X	X		X	X

Abbreviations: OP; oropharynx

- a Full PE mandatory at screening and study discharge (Week 100), otherwise targeted PE as determined by the Investigator or per subject complaints unless signs or symptoms dictate the need for a full PE.
- b Screening vital signs must include a measured height and weight and calculated BMI (Bodyweight in kilograms divided by height in meters squared). Weight will be measured at all dosing visits.
- c Screening 12-lead ECG, complete blood count (CBC), serum electrolytes, blood urea nitrogen (BUN), creatinine (Cr), glucose, ALT, CPK and urinalysis performed within 30 days prior to first dose administration.
- d Negative spot urine pregnancy test is required at screening and prior to each study treatment, vulvoscopy and biopsy/surgical excision.
- e At least 34 mL (4 x 8.5 mL yellow (ACD) tubes) whole blood and 4 mL serum per time point. At least 68 mL whole blood and 8 mL serum should be collected prior to first dose.
- f At least 51 mL [6 x 8.5 mL yellow (ACD) tubes] whole blood and 4 mL serum should be collected at Week 27.
- g HLA testing will be performed once from an existing PBMC sample.
- h HPV genotyping and Pap smears are performed on the same ThinPrep™ cervical specimen.
- i An additional visit may be scheduled to perform vulvoscopy if worsening of disease is suspected. Biopsies should not be performed at any visit other than at entry (Screening), Week 48, and Weeks 74 and 96 for Subgroups C and D unless the investigator suspects invasive cancer. All biopsy samples and/or excision samples must be sent to the PAC for review.
- j Standardized high resolution digital imaging of the vulva and the associated acetowhite stained lesion(s) must be performed prior to and after biopsy, and at all vulvoscopy examinations. Additionally, standardized high resolution digital imaging should be obtained during examinations of the vagina if lesions are identified, for documentation.
- k Tissue specimen and slides from all excised tissue must be reviewed by the PAC and residual vulvar tissue from entry, Week 48, 74 or Week 96 specimen(s) (paraffin blocks or unstained slides) should be sent to the central pathology laboratory for immunohistochemistry (IHC) and HPV testing.
- l HPV genotyping is performed on vulvar tissue specimen using a PCR based assay.
- m Potential dosing at Week 52 and Week 78 is applicable for partial responders only.
- n Subjects will take home imiquimod plus an imiquimod dosing log to document their use of imiquimod. Administration of imiquimod begins on Day 0.
- o A phone call will be used to review the Participant Diary (PD) with subject within 8-14 days following dose 1 and 2. The patient will be expected to bring the PD to the next visit for review.
- p PRO measures (SF-36, EQ-5D-5L) plus two additional questions will be assessed as described in [Section 6.8](#).

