## 6.12 VULVAR HPV TESTING

A 4 mm vulvar punch biopsy sample will be obtained at Screening, Weeks 48, 74, and 96, and will be sent to a central laboratory for HPV genotyping by PCR. In the case of multifocal disease, a 4 mm vulvar biopsy will be obtained from two regions of most advanced and severe disease as judged by the investigator. The subject will be requested to abstain from sexual activity and refrain from use of douching vulvar biopsy samples to eliminate potential interference with the results of HPV testing.

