**Figure 1: Study Visit Schedule**

**Imiquimod treatment** - Subjects randomized to the VGX-3100 with imiquimod arm will apply imiquimod 5% cream to the vulvar lesion(s) beginning in the evening on Day 0, and will continue to apply imiquimod cream three times per week for 20 weeks (inclusive of administration in the evening of VGX-3100 dosing). Subjects unable to tolerate imiquimod treatment may reduce their dosing frequency, and will document their use on the imiquimod dosing log provided.

**Efficacy Assessment:** Biopsies obtained as part of the study at Screening will be from the region of most advanced and severe disease as judged by the Investigator, and must be a minimum of 4 mm in length. Visible lesion must remain after screening biopsy to ensure measurement on study.

[figure not shown]
Visualization of a normal appearing vulva by visual inspection with vulvoscopy is insufficient evidence to confirm disease regression. Disease regression will be based on histopathologic assessment at Week 48, 74, and 96. Subjects will be monitored during the course of the study by vulvoscopy. Lesion(s), defined as areas that stain acetowhite, will be assessed during vulvoscopy at Screening, Day 0, and Weeks 4, 12, 27, 48, 74 and 96. Using standardized high resolution digital imaging, vulvar lesion(s) will also be quantitatively measured at Screening, Day 0, and Weeks 4, 12, 27, 48, 74 and 96.

The decision process following results of the Week 48 biopsy are described in [Figure 2](#) below and as follows: At Week 48, the subject will undergo repeat vulvar punch biopsy/biopsies of the same lesion as study start, but adjacent to the original site within the boundaries of the original lesion (see [Table 3](#) for Minimally Required Biopsy Procedures). If after evaluation of biopsy tissue by the PAC there is no evidence of HSIL (Subgroups A or B), the subject will continue to Week 74 for vulvoscopy, and biopsy adjacent to the site of the initial biopsy. Repeat biopsies that are indicated beyond Week 48 must be taken from the same lesion, adjacent to the prior biopsy site(s) within the boundaries of the original lesion.

If after evaluation of the biopsy tissue HSIL remains, but there is a reduction in lesion size or no change in lesion size from baseline (Subgroups C or D), the Investigator has the option to give the subject a 5th dose of VGX-3100 at Week 52, and the subject will continue on study with vulvoscopy and biopsy at

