**Figure 2: Decision process at Week 52**

The decision process following results of the Week 74 biopsy are described in [Figure 3](#) and as follows: At Week 74, the subject will undergo repeat vulvar punch biopsy/biopsies of the same lesion as study start, but adjacent to the original site within the boundaries of the original lesion (see [Table 3](#)). If after evaluation of biopsy tissue by the PAC there is no evidence of HSIL (Subgroups A or B), the subject will continue to Week 96 for vulvoscopy, and biopsy adjacent to the site of the initial biopsy.

[figure not shown]
If HSIL remains but there is a reduction in lesion size or no change in lesion size from baseline (Subgroups C or D), the Investigator has the option to give the subject a 6th dose of VGX-3100 at Week 78, and the subject will continue on study with vulvoscopy and biopsy at Week 96. Alternatively, the Investigator may choose to treat the subject with surgical or standard treatment, and the subject will continue on study without further biopsy.

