- If any SAE (or potentially life-threatening AE) or death assessed as related to study treatment occurs, further enrollment and study treatment will be halted immediately until a thorough investigation has been conducted by the Medical Monitor, Principal Investigator for the trial, IRB (if applicable) and the DSMB.
- If three or more subjects in this study experience the same Grade 3 or 4 adverse event, assessed as related to study treatment, further enrollment and study treatment will be halted immediately until a thorough investigation has been conducted by the Medical Monitor, Principal Investigator for the trial, and the DSMB.
- In the event of two identical, unexpected, Grade 4 toxicities, assessed as related to study treatment, further enrollment and study treatment will be halted immediately until a thorough investigation has been conducted by the Medical Monitor, Principal Investigator for the trial, IRB (if applicable) and the DSMB.

The sponsor or designee will notify all investigators and IRBs/EC (if required) regarding the outcome of any investigation stemming from a Study Pause.

Immunogenicity Assessment: The study will explore humoral and cell mediated immune responses to VGX-3100, and VGX-3100 with imiquimod, in blood samples taken at baseline (both Screening as well as Day 0 prior to dosing) and at Weeks 15, 27, 48, 74 and 96. Vulvar samples will also be analyzed for evidence of immune responses at Screening and at Weeks 48, 74 and 96.

Virologic Assessment: Tissue samples will be obtained to characterize HPV infection at Screening, Week 48, 74 and 96. Cervical samples, oropharyngeal rinse samples, vaginal, and intra-anal tissue swab samples will be obtained to characterize HPV infection in samples from study subjects taken at Screening (cervical sample only), Day 0 prior to dosing (OP, vaginal and intra-anal only) and at Weeks 27, 48, 74, and 96.

If there is residual tissue in the paraffin block after histologic diagnoses have been rendered, then unstained slides and/or the relevant paraffin blocks will be collected for immunohistochemistry (IHC) and in situ hybridization (ISH) for the presence of HPV-16/18. Whenever possible, these studies will be performed on tissue sections from the diagnostic biopsy (pre-dose) and from tissue obtained post-dose (Week 48, 74 and 96).

HLA haplotyping: A sample from one time point during the study will be tested to explore the relationship between subject HLA haplotypes and regression.

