### 3.2 EFFICACY ASSESSMENT

The efficacy assessment will be based upon histopathology. Visualization of a normal appearing vulva by visual inspection with vulvoscopy is insufficient evidence to confirm disease regression. Disease regression will be based on histopathologic assessment at Week 48, 74 and 96. Subjects will be monitored during the course of the study by vulvoscopy. Lesion(s), defined as areas that stain acetowhite, will be assessed during vulvoscopy at Screening, Day 0, and Weeks 4, 12, 27, 48, 74 and 96 visits. Using standardized high resolution digital imaging, vulvar lesion(s) will also be quantitatively measured at Screening, Day 0, and Weeks 4, 12, 27, 48, 74 and 96.

Biopsies obtained as part of the study at Screening will be from the region of most advanced and severe disease as judged by the Investigator, and must be a minimum of 4 mm in length. Visible lesion must remain after screening biopsy to ensure measurement on study.

The decision process following results of the Week 48 biopsy are described in [Figure 2](#) and are as follows: At Week 48, the subject will undergo repeat vulvar punch biopsy/biopsies of the same lesion as study start, but adjacent to the original site within the boundaries of the original lesion (see [Table 3](#) for Minimally Required Biopsy Procedures). If after evaluation of biopsy tissue by the PAC there is no evidence of HSIL ([Figure 2](#), Subgroups A or B), the subject will continue to Week 74 for vulvoscopy, and biopsy adjacent to the site of initial biopsy.

If after evaluation of the biopsy tissue HSIL remains, but there is a reduction in lesion size or no increase in lesion size from baseline ([Figure 2](#), Subgroups C or D), the Investigator has the option to give the subject a 5th dose of VGX-3100 at Week 52, and the subject will continue on study with vulvoscopy and biopsy at Week 74. Alternatively, the Investigator may choose to treat the subject with surgical or standard treatment, and the subject will continue on study without further biopsy.

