#### 6.2.4 8-14 DAYS POST DOSE 2 PHONE CALL

- Review Adverse Events
- Patient Reported Outcomes
- Review Week 4 PD
  - After completing a review of PD and post treatment injection assessment with the subject on the phone, the Investigator or study personnel will determine whether an office visit is needed for further evaluation.

#### 6.2.5 WEEK 12

The following study evaluations will be performed at Week 12 **prior to study treatment (± 7 days)**:

- Review of concomitant medications and adverse events
- Targeted physical assessment
- Vital signs
- Review imiquimod dosing log and usage (accountability of returned product) for subjects in the imiquimod arm
- Urine pregnancy test
- Vulvoscopy
  - An additional visit may be scheduled to perform vulvoscopy if worsening of disease is suspected. Biopsies should not be performed at any visit other than at entry (screening), Week 48, Week 74 and Week 94 unless PI suspects disease progression. All biopsy samples must be sent to the PAC for review
  - Vulvoscopy visualization of a normal appearing vulva is insufficient evidence to confirm disease regression

- Vulvar Lesion Photography
  - Photographs of the vulva and the associated lesion must be collected.

The following study evaluations will be performed at Week 12 **after study treatment**:

- Post-treatment injection site reaction assessment within 30-45 minutes after study treatment
- Patient Reported Outcomes
- Distribute PD
- Distribute 1 box of imiquimod and the imiquimod dosing log to subjects in the imiquimod arm

Download EP data from device within 24 – 48 hours of study treatment

#### 6.2.6 WEEK 15

The following study evaluations will be performed at Week 15 ( $\pm 7$  days):

- Review Adverse Events
- Review Week 12 Participant Diary
- Patient Reported Outcomes
- Whole blood and serum for immunologic assay

#### 6.2.7 WEEK 24

The following study evaluations will be performed at Week 24 **prior to study treatment ( $\pm 7$  days)**:

- Review of concomitant medications and adverse events
- Review imiquimod dosing log and usage (accountability of returned product) for subjects in the imiquimod arm
- Targeted physical assessment
- Vital signs
- Urine pregnancy test

The following study evaluations will be performed at Week 24 **after study treatment**:

- Post-treatment injection site reaction assessment within 30-45 minutes after study treatment
- Patient Reported Outcomes
- Distribute PD

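### Table 1 footnote i bars Week 74 and 96 biopsies that Section 3.2 requires in Subgroups A and B; separately, early surgery for non-cancer lesion growth can remove a subject from the primary denominator

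*Protocol*

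**What the plan says.** **Biopsy schedule.** Footnote i to Table 1 (version 1.2) states that biopsies "should not be performed at any visit other than at entry (Screening), Week 48, and Weeks 74 and 96 for Subgroups C and D", with an exception only where the investigator suspects invasive cancer. Other parts of the protocol differ:

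- Synopsis, after the Week 48 result, for subjects with no HSIL: "Subgroups A or B), the subject will continue to Week 74 for vulvoscopy, and biopsy adjacent to the site of the initial biopsy".
- Synopsis, after the Week 74 result, for the same group: "Subgroups A or B), the subject will continue to Week 96 for vulvoscopy, and biopsy adjacent to the site of the initial biopsy".
- Section 3.2 repeats both instructions. For Week 48 it says "the subject will continue to Week 74 for vulvoscopy, and biopsy adjacent to the site of initial biopsy".
- Synopsis, Virologic Assessment: "Tissue samples will be obtained to characterize HPV infection at Screening, Week 48, 74 and 96", with no subgroup limit.
- Section 6.12 (version 1.1 text): "A 4 mm vulvar punch biopsy sample will be obtained at Screening, Weeks 48, 74, and 96", again with no limit.
- The Biopsy row of Table 1, its footnote k, and the visit lists for Weeks 27, 74 and 96 set no subgroup limit.
- Section 6.2.5 (Week 12) gives the permitted visits as "Week 48, Week 74 and Week 94 unless PI suspects disease progression". There is no Week 94 visit; this is a clerical error for Week 96.

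**Surgery and the primary endpoint.** The synopsis places any subject whose lesion area increases from baseline, at any time, in Subgroup E. She gets surgery at the investigator's judgement and is followed without further biopsy. Section 1.1.8 also allows excision, ablation or medical therapy when judged necessary. The non-responder definition in Section 3.2.1 and Table 4 covers HSIL, AIS or carcinoma at evaluation, HPV-16/18 at evaluation, and non-study medication for VIN. It does not name surgery or ablation. Section 8.1 bases the primary endpoint on tissue collected at Week 48. Section 8.9 opens the efficacy window 14 days before the visit week. Section 8.4 limits mITT to dosed subjects who have the endpoint, and Section 8.11.6 rules out imputation.

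The version 1.2 text available stops at the heading of Section 6.12, so Section 8 is read from version 1.1. The version 1.2 change list names only the removal of one patient-reported outcome instrument and calls all other changes administrative.

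**The concern.** These are two separate defects.

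First, footnote i is worded as a prohibition, and the opening of Section 6 makes adherence to the Schedule of Events mandatory. A site could therefore withhold a biopsy that Section 3.2 requires. Section 3.2 also says that a normal-looking vulva does not establish regression. Without tissue, the later status of women who had cleared HSIL at Week 48 could not be confirmed, and their later tissue HPV and tissue immune samples would be lost.

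Second, rescue by medication is a failure, while rescue by surgery for non-cancer growth can make the outcome missing and so remove the subject. The women removed are those whose lesions grew, so the omission can only push the reported response rate up. The protocol gives no reason for treating the two kinds of rescue differently.

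**Working it through.** **Inputs.** Arms of 24 and 12 (Section 3). True rates 20% and 28%, historical rate 2%, 90% evaluable, 80% power per arm (Section 8.3). Exact one-sided test at 0.025 in each arm (Section 8.9).

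**The plan's own figure.** Evaluable n is 24 × 0.9 = 21.6 and 12 × 0.9 = 10.8. The pass mark is the smallest r with P(X ≥ r | n, 0.02) < 0.025.

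- VGX-3100 alone: r = 3; power 82.1% at n = 21 and 84.6% at n = 22.
- Combination: r = 2; power 81.7% at n = 10 and 85.8% at n = 11.

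The stated 80% holds as a minimum for each arm.

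**Part 1: who would lose tissue.** Primary responders have no HSIL, so they are a subset of Subgroups A and B. The expected minimum is 0.20 × 21.6 = 4.3 plus 0.28 × 10.8 = 3.0, in total 7.3 of 32.4. That is the minimum number exposed if every site follows the footnote; the loss is 0 if none does.

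**Part 2: how a subject leaves the denominator.**

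1. Vulvoscopy at Weeks 4, 12 and 27 can show growth, which triggers Subgroup E.
2. Surgery follows at the investigator's judgement, and no later biopsy is taken.
3. The window opens at Week 48 minus 14 days = Week 46, so tissue excised earlier is not Week 48 tissue. Ablation yields no tissue at all.
4. Surgery is not a listed reason for non-response. Carcinoma is, so the gap concerns non-cancer growth only.
5. No endpoint and no imputation together mean she is outside mITT.

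**Part 2: size.** The documents give no surgery rate, so these cases are assumptions (Clopper-Pearson intervals):

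| Arm | Women dropped | Rate | 95% CI |
|---|---|---|---|
| VGX-3100 alone | 0 | 4/24 = 16.7% | 4.7 to 37.4 |
| VGX-3100 alone | 2 | 4/22 = 18.2% | 5.2 to 40.3 |
| VGX-3100 alone | 4 | 4/20 = 20.0% | 5.7 to 43.7 |
| Combination | 0 | 3/12 = 25.0% | 5.5 to 57.2 |
| Combination | 1 | 3/11 = 27.3% | 6.0 to 61.0 |

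More generally, if a share s of non-responders is removed, the expected rate becomes p / (p + (1 − p)(1 − s)). For s = 10%, 20% and 30%, a true 20% becomes 21.7%, 23.8% and 26.3%; a true 28% becomes 30.2%, 32.7% and 35.7%.

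**Effect on the test.** The pass mark is 3 for n = 13 to 31 and 2 for n = 2 to 12, so dropping a few subjects does not move it. At a true 2%, starting from n = 22, type I error is 0.9% for s up to 20%, 1.2% at 30% and about 4.6% at 50%; in that last case n often falls to 12 or below. Starting from n = 11 it stays near 2.0%.

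**The case against.** **On Part 1.** Footnote i is attached to the Vulvoscopy row, while the Biopsy row carries footnote k, which has no subgroup limit. Many concordant passages stand against one outlier. Few defined endpoints depend on Week 74 and 96 tissue from women who stop at four doses: the 5- and 6-dose histology endpoint excludes them, and the objective behind the later virologic endpoint concerns more than four doses. All of this is fair, and it limits the consequence to descriptive histology, tissue HPV and tissue immune data. It does not remove the contradiction, because the footnote forbids what Section 3.2 orders.

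**On Part 2.** The strongest reply is that wide-excision specimens go to the Pathology Adjudication Committee, the primary endpoint accepts excised tissue, and Section 3.2.1 speaks of HSIL at evaluation. An early excision showing HSIL might then be read as non-response. An analysis plan could also derive early surgery as failure, which would be endpoint derivation and not imputation. Table 13 (version 1.1) lets a subject with HSIL continue treatment, so not every growing lesion is removed.

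These readings are possible, but none is written as the rule. Section 8.1 ties the endpoint to tissue collected at Week 48, Section 8.9 sets the window, and Section 3.2.1 names medication as the only failing rescue. Table 13 permits continuation without preventing surgery, and the ablation route leaves nothing for the committee to read. Two points stand: the frequency is unknown, and Section 8 is visible only in version 1.1.

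**Conclusion.** Both parts hold. Footnote i contradicts the synopsis and Section 3.2 and is wrong as written. It puts at risk later tissue from at least about 7 of 32 evaluable subjects if followed everywhere, and from none if ignored. It does not affect the primary endpoint, the 5- or 6-dose endpoints, or the photographic lesion-area endpoint.

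The surgery gap can inflate the primary response rate. In the illustrations the shift is 1.5 points with two women dropped (16.7% to 18.2%) and 3.3 points with four (16.7% to 20.0%), both small against the width of the intervals. The superiority decision is not expected to change; only the extreme case of half of all non-responders being removed takes type I error above 2.5% in the VGX-3100 alone arm. This conclusion assumes that Section 8 carried over unchanged into version 1.2.

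**What to change.** - In footnote i, delete the words that limit Weeks 74 and 96 to Subgroups C and D, or make the limit Subgroups A to D.
- In Section 6.2.5, correct Week 94 to Week 96.
- In Section 3.2.1 and Table 4, add surgical or ablative treatment of vulvar HSIL before the Week 48 assessment to the non-responder definition. State that these subjects stay in the mITT denominator.

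The cost is amendment wording. No procedure is added, because Section 3.2 already requires the biopsies. The non-responder rule may lower the reported rate slightly, but power remains adequate even if all of the planned 10% non-evaluable subjects count as failures. With n = 24 and p = 0.9 × 0.20 = 0.18, P(X ≥ 3) = 83.3%. With n = 12 and p = 0.9 × 0.28 = 0.252, P(X ≥ 2) = 84.5%.
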